1.6. Randomization and Masking

Participants will wear all study lenses in a bilateral fashion. There will be three levels of randomization in this study: (1) Sequence of driving time (Day and Night), (2) Sequence of Lens wear (Test, Control 1 and Control 2) and (3) Driving route (A, B and C). Hazard and pedestrian locations will be randomized for each driving route.

Subjects will be first randomly assigned to one of two possible driving time sequences (Day/Night or Night/Day) using a 2x2 crossover design. Within each diving time (Day and Night) subjects will be randomly assigned to one of six possible lens wear sequences using a 3x3 Williams crossover design:

8			
Sequence	Period 1	Period 2	Period 3
1 Test		Control 1	Control 2
2	Test	Control 2	Control 1
3	Control 1	Test	Control 2
4	Control 1	Control 2	Test
5	Control 2	Test	Control 1
6	Control 2	Control 1	Test

Table 3: 3X3 Williams Design

The design is balanced with respect to first order carry-over effect as every treatment follows every other treatment the same number of times.

Within each time and lens type combination subjects will be randomized to a driving route (Route 1, Route 2 and Route 3) to further reduce any potential selection bias. The randomization scheme will be generated using the PROC PLAN procedure from SAS Software Version 9.4 (SAS Institute, Cary, NC). The study site must follow the randomization scheme provided and complete enrollment per the randomization list and not preselect or assign subjects.

Every effort will be made to mask both the subject and the investigator, to reduce potential bias where ever possible. Subjects will be masked to the identity of the investigational product when only a contact lens correction is worn. However, if subjects perceive a change in light level during Test contact lens wear, they may become aware of the product being tested.

Subjects will also be aware of the test condition when the ACUVUE® OASYS® brand contact lenses with HYDRACLEAR® Plus is worn with Transitions® XTRActiveTM- Gray spectacle

frames (Control 2) as the other test conditions will involve contact lens wear with a spectacle frame without spectacle lenses.

Investigators will be involved in the on-road driving data collection (clinical personal within the vehicle) will be partially-masked as to the identity of the investigational product. (i.e. another investigator will fit the contact lens prior to the driving assessment).

Under normal circumstances, the mask should not be broken until all subjects have completed the study and the database is finalized. Otherwise, the mask should be broken only if specific emergency treatment/course of action would be dictated be knowing the treatment status of the subject. In such cases, the investigator may, in an emergency contact the medical monitor. In the event the mask is broken; the sponsor must be informed as soon as possible. The date, time and reason for the unmasking must be documented in the subject record. The investigator is also advised not to reveal the study treatment assignment to the clinical site or sponsor personnel.

2. GENERAL STATISTICAL CONSIDERATIONS

All data summaries and statistical analyses will be performed using the SAS software version 9.4 or higher (SAS Institute, Cary, NC).

Descriptive statistics will be reported for all key variables as appropriate. Continuous data will be summarized descriptively by n, mean, standard deviation (SD), median, minimum (Min) and maximum (Max). Categorical data will be summarized descriptively by frequency count (n) and percentage (%) of subjects or eyes within each category level.

Summaries will be presented by visit and study lens type (Test, Control1, Control2), as applicable, for the analysis population set of interest. The denominator for all percentages will be the number of subjects (or eyes as applicable) with available data in the group/lens under consideration. Unscheduled visits will be summarized separately and will be excluded from the primary and secondary analysis.

The primary analysis will be conducted using the GLIMMIX Procedure (SAS/STAT 14.2, SAS Institute, Cary, NC). See **Error! Reference source not found.** for more details.

2.1. Level of Statistical Significance

All planned analysis will be conducted with an overall type I error rate of 5%. Unless otherwise specified, all statistical tests will be 2-sided.

2.2. Analysis Sets

The study participants will consist of Open licensed drivers (aged 20-49 years) with more than one year of driving experience. Participants must be regular drivers with best-corrected monocular visual acuity of 20/20 (logMAR 0.00) or better in each eye. Participants must be regular soft contact lens wearers with refractive errors within the range of available study contact lenses supplied by JJVC with uncorrected astigmatism of no more than 1.00 DC.

The following three populations will be defined and used in the analysis and presentation of the data.

2.2.1. All Enrolled

All Enrolled Population includes all consented subjects with recorded data in the electronic Case Report Form (eCRF) database.

2.2.2. Per-Protocol Population

The Per-protocol population will consist of all subjects who have successfully completed all visits and did not substantially deviate from the protocol as determined by the trial cohort review committee prior to database hard lock. Justification of excluding subjects with protocol deviations in the per-protocol population set will be documented in a memo to file.

2.2.3. Safety Analysis Set

Safety population be comprised of all subjects who were administered any test article excluding who drop out prior to administering any test article. At least one observation for safety endpoints should be recorded (e.g. slit-lamp finding, adverse events ... etc.) or on after lens insertion start date.

Subjects will be analyzed as per treatment received.

2.3. Data Handling Rules

Missing or spurious values will not be imputed as the number of missing values is expected to be low. The count of missing values will be included in the summary tables and listings. Dropout is expected to be one of the main reasons of missing data in the trial. Past soft contact lens trials don't provide any evidence that subject dropout is systematic or not at random.

2.4. Definition of Subgroups

No subgroup analysis is planned in this study.

2.5. Covariate Adjustment

All models will be adjusted for age and gender as fixed covariates. If these factors are not significant at the 15% significance level they will be removed from the final model.

3. INTERIM ANALYSIS AND DATA MONITORING

There will be no interim analysis.

Adverse events, protocol deviations, and product complaints will be monitored throughout the study. For the purposes of this study the following definitions will apply:

Adverse Event: any untoward medical occurrence in a patient or clinical investigation subject administered a test article whether or not caused by the test article or treatment.

Protocol Deviation: any change, divergence, or departure from the study design or procedures of a research protocol that is under the investigator's control and that has not been approved by the IRB.

Product Complaint: any written, electronic, or oral communication that alleges deficiencies related to the identity, quality, durability, reliability, safety, effectiveness, or performance of a product after it is released for clinical trial use.

4. SUBJECT INFORMATION

4.1. Demographics and Baseline Characteristics

Demographic characteristics will be summarized on safety, per-protocol and all enrolled population using descriptive statistics for continuous variables, and numbers and percentages of subjects for categorical variables. Demographic information will include age, sex, race, ethnicity and iris color.

Age is calculated in accomplished years at informed consent date.

The following baseline characteristics will be summarized at eye level:

- Monocular and binocular subjective spherocylindrical refractions on LogMAR scale
- Monocular and binocular Subjective best sphere refractions (logMAR)

4.2. Disposition Information

A disposition of subjects including the number and percentage of subjects enrolled, subjects adhering to protocol (PP population), subjects treated (safety population), subjects completed, subjects discontinued from the study and subjects enrolled but not dispensed will be summarized.

Enrolled subjects will be allocated to one of the three mutually exclusive groups:

- 1. Completed: Subjects are considered to have completed the study if they (i) provided informed consent, (ii) they are eligible and (iii) have completed all visits through Visit 4.
- 2. Discontinued: Subjects are considered to have discontinued from the study if (i) test article was administered and (ii) discontinued from the study. Reasons for discontinuation include: (a) Subject's death during the study (b) subject withdrawal of consent (c) Subject not compliant to protocol (d) subject lost to follow-up (e) subject no longer meets eligibility criteria (f) subject develops significant or serious adverse events causing discontinuation of study lens wear (e.g. an event during a measurement session at any visit) (g) subjects who have experienced a corneal infiltrative event (h) investigators clinical judgement regarding the subject safety reasons (that it is in the best interest of the subject to stop treatment) (i) lack of efficacy and safety including lens handling difficulties, poor vision, poor comfort, or unacceptable fit.

- 3. Total dispensed: Total number subjects for which test articles were administered (Completed + Discontinued)
- 4. Enrolled but Not Dispensed: Subjects are considered to be Enrolled Not Dispensed Subjects if they were (i) enrolled to the study (provided informed consent) but failed to satisfy the eligibility criteria (inclusion/exclusion criteria) or (ii) if they are randomized but did not receive a test article.
- 5. Total enrolled: Completed + Discontinued + Enrolled but Not Dispensed

The percentage will be calculated using total enrolled as denominator.

4.3. Protocol Deviations

Any protocol deviation that could impact the primary endpoints will result in the subject being excluded from the Per-Protocol analysis population. No analysis on protocol deviations will be performed. All reported protocol deviations will be listed.

4.4. Medical History

A listing of medical and surgical history will be created for all enrolled subjects.

4.5. Prior and Concomitant Medications

Prior and concomitant medications will be documented during screening and updated during the study when applicable.

Disallowed medications or any concomitant therapies that are disallowed for this study include: Any ocular medications or any systemic medications that are known to interfere with contact lens wear.

A listing for both prior and concomitant medications will be created for all enrolled subjects.

4.6. Reasons for Discontinuation

Primary reasons for discontinuation, if any, will be tabulated using frequency count and percentage n (%) using the following categories:

- Adverse event (AE)
- Unsatisfactory Visual Response due to test article
- Unsatisfactory Lens Fitting due to test article
- Lens Discomfort
- Lens Handling Difficulties
- Withdrew Consent during study
- Lost to Follow Up

- Subject no longer meets Eligibility Criteria
- Subject Withdrawn by PI due to noncompliance to protocol
- Test Article No Longer Available
- Others

A listing of discontinued subjects will be created including lens type being used at time of discontinuation. Reasons for discontinuations categorized as Others will be specified in the listing.

5. PRIMARY ENDPOINTS

All the primary endpoints analyses will be conducted on PP population comparing the Test lens to Control lenses. Additional sensitivity analysis will be conducted on all subjects who were administered any test article excluding subjects who drop out prior to administering any test article. At least one observation should be recorded.

5.1. Definition

Overall driving performance score:

A closed road driving circuit environment will be used to evaluate the effects of the Test lens on night and day time driving performance. This approach involves driving a real vehicle on a closed road circuit (closed to all traffic except QUT vehicles), the driving environment can be modified to closely resemble real on-road conditions and safety can be assured. Quantitative methods will be used to assess vision and driving performance under a range of challenging conditions and appropriate masking, order of testing, randomization and control conditions will be used.

Overall driving performance score is a composite score calculated as the mean of the Z-scores of the following six driving measures: average sign recognition distance (in meters), percentage of correctly identified sign (\sim 42 signs), percentage of hazard avoidance/detection (9 hazards), average pedestrian recognition distance (in meters), lane keeping (percentage of time inside the lane) and the inverse of driving lap time (in seconds). Equal weighting will be assigned to each measure. Where necessary the individual Z scores will be transformed (inverted) such that positive Z scores relate to better performance than the mean. This approach captures participants' performance relative to the group as a whole across conditions and takes into consideration the fact that some tasks may be prioritized over others during driving (Wood JM.; 2002).

Overall driving performance will be calculated for each participant by test article (Test, Control 1 and Control 2) and driving time (day and night).

5.2. Primary Analysis Methods

Overall driving performance score will be analyzed using a linear mixed model; sequence of lens wear, period, lens type, first order carry-over, driving time (day or night) and the 2-way interactions: lens*time, sequence*time, period*time and carry*time will be included in the model as fixed effects. Age will be included as fixed covariate when appropriate. An appropriate covariance structure will be selected to model the correlation between measurements across periods within the same subject and driving time. Covariance structures that will be considered include:

- Compound Symmetry (CS)
- Heterogeneous Compound Symmetry (CSH)
- Unstructured (UN)
- Ante-dependence (ANTE(1))

For ANTE(1) structure, subject and driving time nested within subject will be included in the model as random effects. For the remaining structures only subject will be included as random effect. The covariance structure that returns the lowest Akaike Information Criteria Corrected (AICC) will be selected as the structure that best fit the data¹². Heterogeneous residuals covariance structures (R-side) across driving time will be considered when appropriate. The log-likelihood ratio test will be used to test for the homogeneity between the residual covariance structures. The Kenward and Roger method will be used for the denominator degree of freedom. Non-significant interactions at the 15% significance level will be excluded from the model. The interaction between lens type and driving time will be forced into the final model.

Comparisons between Test and Control 1 will be conducted overall across driving time and within each level of driving time. Results from the final selected model will be reported as least-square mean (LSM) differences with 95% confidence intervals.

The null and alternative hypotheses for non-inferiority of Test lens relative to Control 1 are as follows:

$$H_0: \mu_T - \mu_C \le -0.25 H_A: \mu_T - \mu_C > -0.25,$$

where μ_T and μ_C are the means of night driving performance score for Test and Control 1, respectively. Non-inferiority of the Test relative to Control 1 will be concluded if the lower limit of the 95% confidence interval of the LSM difference between Test and Control 1, at night driving time, is greater than - 0.25.

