5. TEST ARTICLE ALLOCATION AND MASKING

5.1. Test Article Allocation

Participants will wear all study lenses in a bilateral fashion. There will be three levels of randomization in this study: (1) Sequence of driving time (Day and Night) (2) Sequence of lens wear (Test, Control1 and Control2) and (3) Driving Route (A, B, C). Hazard and pedestrian locations will be randomized for each driving route.

Subjects will be first randomly assigned to one of two possible driving time sequences (Day/Night and Night/Day) using a 2x2 crossover design. Within each driving time (Day and Night) subjects will be randomly assigned to one of six possible lens wear sequences using a 3x3 Williams crossover design:

Table 1: 3x3 Williams design

Sequence	Period1	Period 2	Period 3
1	Test	Control 1	Control 2
2	Test	Control 2	Control 1
3	Control 1	Test	Control 2
4	Control 1	Control 2	Test
5	Control 2	Test	Control 1
6	Control 2	Control 1	Test

This design is balanced with respect to first carry-over effect as every treatment follows every other treatment the same number of times.

Within each time and lens type combination subjects will be randomized to a driving route (Route1, Route2 and Route3) to further reduce the potential for treatment bias. The randomization scheme will be generated using the PROC PLAN procedure from SAS Software Version 9.4 or higher (SAS Institute, Cary, NC). The study site must follow the randomization scheme provided and complete enrollment according to the randomization list and not pre-select or assign subjects.

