3.6.	Randomization	
Refer to pre-determined randomization order of testing (counter balancing) for the three test treatments. The final contact lens powers found in Visit 1 will be used.
 
 • Test contact lenses (worn with spectacle frame without lenses) • OASYS clear contact lenses (worn with spectacle frame without lenses) • OASYS clear contact lenses (worn with photochromic spectacles) 	
3.7.	Lens Insertion	
The Investigator or the subject inserts the study lenses. Record the time of lens insertion. Check for lens damage under the slit lamp before proceeding with lens settling. Replace damaged lenses if applicable.
	
3.8.	Lens Settling	
Allow the study lenses to settle for a minimum of 15 minutes.
 
Note: for nighttime testing, sufficient time is allowed for the subject to dark adapt.
	
3.9.	Pupillometry	
Measure the right eye pupil diameter during distance fixation (3 measures) using NeurOptics Pupillometer while subject seated in vehicle.
 
EDC: record pupil diameters in mm (0.1 mm increments)
	
3.10.	Illuminance levels	
Measurement of lighting level on the track outside the vehicle and at the plane of the eye in the vehicle.
 
 • For daytime testing, the illuminance must be > 1000 lux. • For nighttime testing, the illuminance must be < 10 lux. 
EDC: record outside and inside illuminance in lux rounded to the nearest whole number.
	

Visit 3: Closed-circuit on-road driving performance 1 (Day/night condition based on randomization)			
Step	Procedure	Details	
3.11.	Driving assessment	
Subject performs three laps of the circuit while under assessment. Measurements recorded include:
 
 1. Sign recognition 
 a. EDC: record % signs correctly identified b. EDC: record distance to signs in meters 2. Hazard avoidance 
 a. EDC: record % hazards hit 3. Driving time 
 a. EDC: record lap time in seconds b. EDC: record the % time in wrong lane 4. Pedestrian recognition distance 
 a. EDC: record distance to recognition in meters 
A composite driving Z score will be calculated afterwards using measures listed above.
	
3.12.	Subjective Questionnaire	Administer subjective questionnaire regarding driving task just completed. This will be a paper-administered questionnaire.	Appendix A

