3.13.	Lens Removal	The study lenses will be removed and discarded. A fresh pair of lenses will be used for each trial.	
3.14.	Test Treatments 2 and 3	Repeat steps 3.6 to 3.13 for the other testing treatments until all three have been completed.	

Visit 3: Closed-circuit on-road driving performance 1 (Day/night condition based on randomization)			
Step	Procedure	Details	
3.15.	Exit Slit Lamp Findings	
FDA Slit Lamp Classification Scale will be used to grade the findings.
 
If any of these slit lamp findings are grade 3 or higher, the subject is classified as having an adverse event. Adverse events shall be documented and followed until resolved, at which time they will be terminated from the study.
 
If the clearance of the fluorescein needs to be expedited, preservative-free rewetting drops or saline may be instilled.
	
3.16.	Exit Visual Acuity	
Record the distance logMAR visual acuity (OD, OS, and OU) to the nearest letter with their habitual correction in place. Subjects must read the smallest line until at least 50% of the letters are read incorrectly.
 
EDC: record logMAR acuity
	

VISIT 4

Visit 4: Closed-circuit on-road driving performance 2 (Day/night condition based on randomization)			
Step	Procedure	Details	
4.1.	As per Visit 3	Visit 4 follows the same procedures outlined in Visit 3, but is conducted under the opposite condition to Visit 3 (day/night).	

FINAL EVALUATION

The final evaluation will ordinarily take place immediately following the last scheduled follow-up visit per the study protocol. It may also take place at any point the subject discontinues the study or is terminated from the study.

Final Evaluation			
Step	Procedure	Details	
F.1	Final Exam Form	Indicate if the subject completed the study successfully. If subject discontinued from the study indicate the reason.	
F.2	Exit Visual Acuity	Record the distance logMAR visual acuity (OD, OS, and OU) to the nearest letter with their habitual correction in place. Subjects must read the smallest line until at least 50% of the letters are read incorrectly. EDC: record logMAR acuity	

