We used independent vague normal N(0,1000) priors for the regression coefficients β , vague inverse-gamma with shape and scale parameters of 0.001 for the variance parameter σ^2 . The Metropolis sampler algorithm as implemented in the SAS MCMC Procedure (SAS/STAT 14.1, SAS Institute, 2015) was used to carry out parameter estimation. After a burn-in of 80,000 iterations, we run the algorithm for additional 500,000 iterations with a thinning factor of 100 to allow posterior chains of estimated parameters to converge. Convergence of the simulated chains was assessed using autocorrelation and sample trace plots.

The posterior mean difference in driving performance between corrected and uncorrected vision was estimated to be 0.579 with 95% credible interval (95% CrI) of (0.249, 0.917). The estimated variance was 0.0483 with 95% CrI of (0.0051, 0.1692).

With a sample size of 24 subjects, the estimated power for different scenarios of intra-class correlation (ICC) is shown in the table below:

Table 2. Statistical Fower by ICC						
Intra-class correlation	Between subject	Effect size	Power (%)			
(ICC)	variance σ^2					
.40	0.05	0.25	71			
.50	0.05	0.25	85			
.60	0.05	0.25	95			

 Table 2: Statistical Power by ICC

The sample size calculation was conducted using the PROC POWER Procedure (SAS/STAT 14.1, SAS Institute, 2015). The non-inferiority hypothesis testing problem of a 3x3 crossover design was formulated as a two-sample non-inferiority hypothesis testing (Peng Sun, 2010).

As discussed above, the estimated posterior mean difference in driving performance between corrected vision (treated) and uncorrected vision (untreated) was estimated to be 0.579 with 95% credible interval (95% CrI) of (0.249, 0.917). We therefore used the lower bound of the 95% credible interval as the non-inferiority margin (\sim -0.25). This represents a discount of 43% from the estimated difference between corrected vision and uncorrected vision.

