6.1. Definition

Binocular visual performance:

The following measurements will be used to assess the performance of the test and control products in a controlled laboratory setting which simulate a wide range of visual conditions encountered while driving.

1. High luminance (~500 lux) high contrast (90%) LogMAR distance visual acuity

- 2. High luminance (~500 lux) low contrast (10%) LogMAR distance visual acuity
- 3. Low luminance (~1 lux) high contrast (90%) LogMAR distance visual acuity
- 4. High luminance (~500 lux) contrast threshold (Pelli-Robson chart)
- 5. Low luminance (~1 lux) contrast threshold (Mesotest II instrument by Oculus, Germany)

The order of the vision tests will be randomized for each condition. The ETDRS logMAR chart will be used, which is scored on a letter by letter basis (-0.02 log units per letter correctly identified). A number of different EDTRS charts will be used to reduce potential learning effects. Letter contrast sensitivity will also be determined binocularly using the Pelli-Robson chart, scored on a letter by letter basis (0.05 log units per each letter correctly identified). The ETDRS logMAR chart and the Pelli-Robson contrast sensitivity chart are validated techniques routinely used in research to accurately quantify visual performance. Room illuminance will be controlled using dimmer switches and quantified using a lux meter.

There will be two secondary endpoints considered from binocular visual performance evaluation:

- Low luminance ~1 lux) high contrast (90%) distance visual acuity
- Low luminance (~1 lux) contrast threshold

During low luminance contrast threshold evaluation, five Landolt C targets in random orientation will be presented for each of the four contrast levels 95%, 80%, 63% and 50%. Participants will be asked to correctly identify the orientation of the Landolt C. The number of correct response will be recorded for each contrast level. This entire test will be done with and without the presence of a glare source.

Sign recognition (percentage)

Participants will be instructed to report the identity of a percentage of the standard road signs (typically about 42 signs dependent on the route travelled) containing about 65 items of information as they drive around the circuit. We will also measure the recognition distance using the in-vehicle measurement system for one specific road sign while the participant is driving.

Hazard avoidance:

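### Driving route is randomised but absent from every driving model; if each assessment uses one route, any route difference is an avoidable loss of precision

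*SAP*

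**What the plan says.** SAP Section 1.6 makes route the third level of randomisation: "Within each time and lens type combination subjects will be randomized to a driving route (Route 1, Route 2 and Route 3"). Protocol Section 5.1 has the same rule.

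No driving analysis uses it. The primary model (SAP Section 5.2) contains "sequence of lens wear, period, lens type, first order carry-over, driving time (day or night) and the 2-way interactions" of lens, sequence, period and carry-over with driving time. The sign %, hazard %, pedestrian-distance and sign-distance models in Section 6.2 have the same structure. The Appendix A code defines no route variable, and driveseq there is the lens-wear sequence.

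The composite does not remove route either. Its Z-scores express "performance relative to the group as a whole across conditions" (SAP Section 5.1), not performance within route.

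On conduct, Protocol Section 7.2 step 3.11 says "Subject performs three laps of the circuit while under assessment", and step 3.14 says "Repeat steps 3.6 to 3.13 for the other testing treatments until all three have been completed". Read together, three laps feed one lens score. Neither document says whether those three laps share the assigned route.

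**The concern.** Route varies within a subject and within a driving session, so the random subject effect cannot absorb it. Randomising route protects against systematic bias. It does not remove the variance that unequal routes add; only a model term does that. The primary decision needs the lower 95% limit of the night Test minus Control 1 difference to lie above -0.25, so extra residual variance works directly against a lens that is truly non-inferior.

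The same extra noise widens the intervals for the secondary driving endpoints.

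**Working it through.** **Inputs.** From SAP Sections 1.4 and 1.5: 24 completers, margin 0.25, true difference 0, between-subject variance 0.05, ICC 0.40/0.50/0.60 with stated power 71/85/95%. Within-subject variance is s² = 0.05 × (1 - ICC)/ICC, which is 0.05 at ICC 0.50. The size of any route effect is an assumption.

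**1. The plan's own figure.** The SAP says "With a sample size of 24 subjects, the estimated power for different scenarios of intra-class correlation (ICC) is shown" in Table 2, using a two-sample formulation. With 12 per group, SE = √(2 × 0.05/12) = 0.0913 and 0.25/SE = 2.74. On 22 df at one-sided 0.05 this gives 84.3%; ICC 0.40 and 0.60 give 69.9% and 94.6%. All are within 2 points of Table 2. The 12-per-group, one-sided 0.05 reading is inferred. At the stated two-sided 0.05 the same formula gives 74.5% at ICC 0.50.

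**2. Baseline under the planned crossover model.** With lens, period and carry-over fitted in the Williams design, Var(Test - Control 1) = 2.5 × s²/24. Residual df for day and night together are 144 - 48 subject-session blocks - 12 = 84, and t(0.975, 84) = 1.989.
- s² = 0.05: SE = 0.0722, half-width 0.1435, power 92.8%.
- s² = 0.0653, chosen to return the SAP's 85%: SE = 0.0825, power 85.0%.

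**3. Route omitted.** Let the route effects be (-d, 0, +d) with one route per assessment. If each subject drives each route once per session, the added within-subject variance is d². If routes are drawn independently, it is 2d²/3. For d = 0.1 these are 0.0100 and 0.0067.

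| s² | Route scheme | Variance with route in error | Power, formula | Power, simulated |
|---|---|---|---|---|
| 0.05 | each route once | 0.0600 | 87.8% | 87.5% |
| 0.05 | independent | 0.0567 | 89.6% | 89.7% |
| 0.0653 | each route once | 0.0753 | 79.7% | 79.7% |
| 0.0653 | independent | 0.0720 | 81.4% | 80.1% |

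The simulations used 3,000 trials per scenario (Monte Carlo SE about 0.4-0.9 points). The mean night estimate was within 0.005 of zero throughout.

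**4. Interval width.** At s² = 0.05 and d = 0.1 the ratio to the no-route-effect width is √(0.06/0.05) = 1.095 or √(0.0567/0.05) = 1.065. A separate simulation (400 runs per setting) set the standard deviation of the three route effects to 0.10, which is slightly larger (d = 0.10 × √1.5 = 0.122). Across ICC 0.40-0.60 and both schemes, omitting route widened the night interval by about 5-18%; at ICC 0.50 it was 12% (0.162 against 0.144) and 8%. Coverage stayed near 95% with and without route.

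**5. Route modelled.** As a main effect (82 df) at ICC 0.50, the half-width is about 0.145 whatever the route effect. That implies SE of about 0.073 and power of about 92%. In the 3,000-trial simulations, with route plus a route-by-time term kept at p < 0.15, power at d = 0.1 was 92.2% (independent) and 91.9% (each route once) at s² = 0.05, and 82.8% and 84.0% at s² = 0.0653.

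**6. Break-even and no effect.** At d = 0.05 and s² = 0.0653, power without/with route was 84.1/84.4 and 83.3/83.4. With no route effect, the half-width goes from 0.143 to 0.145 (about 1%), and power falls by about 0.5-2 points.

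**7. Other lap readings.** If the laps of an assessment cover all three routes, loss and gain are both zero. If each lap's route were drawn independently, the 85% baseline would fall only to 84.0% at d = 0.1.

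**The case against.** The strongest reply is that nothing in the plan is wrong. Route is randomised to limit bias, randomisation achieves that without a model term, and adjustment is a choice. That stands: this is a precision point only.

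The second reply is that the harm needs two things the documents do not establish. Routes must differ in difficulty, and each assessment must use one route. The only hint of a difference is "typically about 42 signs dependent on the route travelled" (SAP Section 6.1). Sign recognition is scored as a percentage, so a differing count says nothing about difficulty. Moreover, d = 0.1 is a spread of 0.2 in a mean of six Z-scores, which requires most components to move the same way. This also stands, and it is why the size is given as an illustration. The singular wording of the randomisation rule favours one route per assessment, but step 3.11 leaves it open.

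Three stronger readings are tempting and are not supported:
- *The omission uses up the trial's power reserve.* This holds only if the within-subject variance is raised to 0.0653 to force the planned model to 85%. At 0.05, power with d = 0.1 remains about 87-90%, above the 80% target. The gap between 93% and 85% may reflect how Table 2 was computed (step 1), not extra variance.
- *The omission drives the secondary conclusions of no difference.* Those follow from concluding no difference whenever the interval contains the null value. Wider intervals add to that weakness but are not its source.
- *The odds ratios are distorted.* In the logit-link models, omitting route can change the odds ratio being estimated. With a within-route value of 0.70, 70% correct on average and routes at 64.5/70/75% correct, the change is to 0.702, which is negligible.

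**Conclusion.** The omission is certain; its consequence is conditional. If each assessment is driven on one assigned route and routes differ, the difference inflates the error of the night Test minus Control 1 contrast. The linear estimate remains unbiased and the planned analysis remains valid.

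With route effects of about 0.1 composite units, an assumed value, the night interval is roughly 5-18% wider. Power goes from about 93% to about 87-90% at s² = 0.05, or from 85% to about 80% if the variance is matched to Table 2. Below about 0.05 there is nothing to gain. These figures rest on 24 completers, no true difference and a common residual variance; selection among the four covariance structures was not simulated.

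This is a cheap improvement worth making before unmasking, because adding route afterwards would look data-driven.

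**What to change.** 1. State whether all laps in Protocol step 3.11 are driven on the route assigned to that driving time and lens, and whether a subject drives each route once per session.
2. If each assessment uses one route, add assigned route (three levels) as a prespecified fixed main effect to the text and the Appendix A code of the composite, pedestrian-distance, sign-distance, sign % and hazard % models. Keep the existing fallback to compound symmetry in the sign % and hazard % models if they fail to converge. A route-by-driving-time term is optional.
3. If the laps of each assessment cover all routes, leave the models unchanged and say in the SAP that route is averaged within each score.

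**Cost.** 2 df (84 to 82). If routes are equivalent, the interval is about 1% wider and power about 0.5-2 points lower; the power figure comes from simulations that also allowed the optional interaction. No new data are needed for assigned route, which is on the randomisation list. The route actually driven is not among the items recorded at step 3.11, so the term would rest on assignment. Variation from hazard positions that change between trials would remain in the error.
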